4.1.2.2 Central radiology review of locally assessed disease progression

In case patients have equivocal disease progression according to RECIST 1.1 (in the brain, outside of the brain or both) as determined by the investigator, a confirmatory tumor assessment should be done at least 4 weeks thereafter. While the investigator is waiting for the confirmatory tumor assessment, it is preferable that the patient continue on study treatment for as long as it is clinically acceptable. However, during this time, the investigator should do whatever is medically necessary for the patient.

If the investigator does not determine disease progression, the patient should continue receiving the study drug unless there is a medical need (i.e., rapid progression or clinical deterioration) for an immediate change in therapy.

If the investigator confirms disease progression, then the patient will discontinue study drug and subsequent follow-up tumor assessments will no longer be required (except in the cases described below).

Exceptions to the discontinuation of study treatment after progressive disease (PD) being confirmed by the investigator are:

- In case of isolated brain progression with controlled disease outside of the brain, patients may continue the study drug during the treatment of the new brain lesion if appropriate. If

ceritinib has to be interrupted during the treatment of the new brain lesions, it may be resumed after the treatment of the brain lesion if:

- Brain lesions are demonstrated to be controlled by gadolinium-enhanced MRI and if patient is neurologically stable within the last 2 weeks prior to the re-initiation of study drug.
- The disease outside of the brain remains controlled prior to re-initiation of study drug. A new tumor assessment will be repeated if the last one available is older than 4 weeks.
- Time interval between last dose and re-initiation of study drug does not exceed 8 weeks.
- Patient will continue to be followed for safety and efficacy assessments as per schedule of assessment.
- If patient had PD outside of the brain (with minimally symptomatic or no PD in the brain) but still derives clinical benefit from ceritinib following investigator's judgment, patient may continue study drug and continue to be followed for safety and efficacy assessments as per schedule of assessment.

[figure not shown]
[figure not shown]

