6.4.1.5 Palliative radiotherapy and surgery

Local radiotherapy for analgesic purposes or for lytic lesions at risk of fracture, or for progression of the brain metastases may be carried out if required. If palliative radiotherapy is initiated after start of study treatment, the reason for its use must be clearly documented and progression as per RECIST 1.1 must be assessed and documented.

For patients with a RECIST-documented PD into the brain that are candidates to continue study drug beyond progression (see [Section 6.1.3](#) for exceptions to study drug discontinuation), as determined by the Investigator, may undergo radiotherapy and/or surgical resection as palliative localized therapy to treat metastatic lesions.

In any situation, when radiotherapy or surgery is required, ceritinib should be held for at least 4 days prior to radiotherapy and at least 1 day prior to any surgery and may be resumed ≥ 3 days after completing radiotherapy or minor surgery, and ≥ 2 weeks after major surgery.

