7.1.6.3 Survival follow-up

All patients who had PD as per investigator assessment, have started a new anti-neoplastic therapy, and/or withdrew consent from further study assessments will subsequently be followed for survival information every 12 weeks until death, lost to follow-up or withdrawal of consent for survival follow-up. The investigator or his designee will collect this survival

information and any new anti-neoplastic therapies for all patients until the final survival analysis.

Follow-up can be done via a phone contact. Antineoplastic therapies will be captured on the 'Antineoplastic therapies since discontinuation of study treatment' eCRF page following the last dose of the study treatment.

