### **Best overall response**

The BOR will be assessed based on reported lesion responses at different evaluation time points. Both CR and PR must be confirmed by repeat assessments performed not less than 4 weeks after the criteria for response are first met. The next scheduled assessment may be used for purposes of confirmation of response.

BOR for each patient is determined from the sequence of overall (lesion) responses according to the following rules:

- CR = at least two determinations of CR at least 4 weeks apart before progression  
PR = at least two determinations of PR or better at least 4 weeks apart before progression (and not qualifying as a CR)
- SD = at least one SD assessment (or better) > 7 weeks after start of study drug (and not qualifying as a CR or PR)
- PD = progression  $\leq$  17 weeks after start of study drug (and not qualifying as a CR, PR or SD)
- UNK = all other cases (i.e. not qualifying for confirmed CR or PR and without SD after more than 7 weeks or progression within the first 17 weeks)

The cut-off for SD too early and PD too late were chosen based on tumor assessment schedule. Only tumor assessments performed before the start of any further anti-neoplastic therapies (i.e. any additional secondary anti-neoplastic therapy or anti-cancer surgery) will be considered in

the assessment of BOR. If a patient receives any further anti-neoplastic therapy while on study, any subsequent assessments will be excluded from the BOR determination. Further anti-neoplastic therapies will be identified from the data collected on ‘Anti-neoplastic therapies since last date of study drug’ as appropriate. Clinical deterioration will not be considered as documented disease progression. Patients with BOR ‘unknown’ will be summarized by reason for having unknown status. The following reasons will be used:

- No valid post-baseline assessment
- All post-baseline assessments have overall response UNK
- New anti-neoplastic therapy started before first post-baseline assessment
- Stable disease (SD) too early ( $\leq 7$  weeks after start date of study drug)
- PD too late ( $> 17$  weeks after start date of study drug).

Special (and rare) cases where BOR is ‘unknown’ due to both early SD and late PD will be classified as ‘SD too early’. In case, a patient had only a non-measurable disease at baseline, same cut-off ( $\leq 7$  weeks after start date of study drug) will be applied for a response of non - CR/non-PD too early.

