### **Determination of missing adequate tumor assessments**

For the computation of ORR (for primary analysis), patients without any radiological assessment after the start date of study drug will be counted as failure.

Partial or complete responses reported prior to any additional anticancer therapy will be considered for ORR computation irrespective of the number of missed assessments before response. The anticancer therapy will be defined for intracranial, extracranial and whole body separately: e.g., radiotherapy to the brain will only be considered as anticancer therapy for intracranial and whole body endpoints but not for extracranial endpoint. In this section, the ‘missing adequate assessment’ is defined as assessment not done or assessment with overall lesion response equal to UNK. For the sake of simplicity, the ‘missing adequate assessment’ will also be referred as ‘missing assessment’.

As detailed in [Section 14](#) (Appendix 2) of the LDK378A2205 protocol and [Table 2-2](#) of SAP, the PFS censoring and event date options depend on the presence and the number of missing tumor assessments. *For example, an event occurring after two or more missing assessments is censored in the analysis of PFS at the last adequate tumor assessment before the event date.*

An exact rule to determine whether there is none, one or two missing assessments is therefore needed. This rule will be based on the distance between the last adequate tumor assessment date and the event date.

If the distance is larger than threshold  $D_1$  or  $D_2$  then the analysis will assume one or two missing assessments, respectively. The threshold  $D_1$  will be defined as the protocol specified interval between the tumor assessments plus the protocol allowed window around the assessments. Similarly, the threshold  $D_2$  is defined as two times the protocol specified interval between the tumor assessments plus the protocol allowed window around the assessments. In this study, the protocol defined schedule of tumor assessment is every 8 weeks and each assessment is expected to be performed at the scheduled time point plus or minus 1 week, i.e. the window is 2 weeks, then any distance larger than  $D_1 = 8 + 2 = 10$  weeks means one missing assessment and any distance larger than  $D_2 = (2 * 8) + 2 = 18$  weeks means two missing assessments.

The same definition of  $D_2$  will be used to determine the PFS censoring reason.

Possible censoring reasons for PFS are:

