##### Post therapies

###### Start date:

Imputed date = max (last date of study drug + 1, first day of the month), if day is missing;

Imputed date = max (last date of study drug + 1, 01JAN), if day and month are missing.

End date: No imputation.

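### The best-overall-response rule excludes scans after on-study anticancer therapy, but the one data source it names starts after the last dose and so misses local brain therapy given on treatment

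*SAP*

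**What the plan says.** **The exclusion.** SAP 2.7.1 (Best overall response) admits "Only tumor assessments performed before the start of any further anti-neoplastic therapies" to BOR, and adds: "If a patient receives any further anti-neoplastic therapy while on study, any subsequent assessments will be excluded from the BOR determination".

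**What counts.** SAP 4.6.1 defines anticancer therapy separately by site: "radiotherapy to the brain will only be considered as anticancer therapy for intracranial and whole body endpoints but not for extracranial endpoint". It gives no data source for this.

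**Where it is read from.** SAP 2.7.1 continues: "Further anti-neoplastic therapies will be identified from the data collected on" the page for anticancer therapy since the last date of study drug. The sentence ends with the qualifier *as appropriate* and names no other source.

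**What that page covers.** Protocol 7.1.6.3 describes therapies captured on the post-discontinuation "eCRF page following the last dose of the study treatment". SAP 4.8.4 handles partial start dates for post-treatment therapies in the same spirit: "Imputed date = max (last date of study drug + 1, first day of the month), if day is missing".

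**What may happen before the last dose.** Under Protocol 4.1.2.2, in isolated brain progression, "patients may continue the study drug during the treatment of the new brain lesion if appropriate". Sections 6.1.3 and 7.1.4.1 allow ceritinib to be resumed after the brain lesion has been treated. Section 6.4.1.5 adds: "Local radiotherapy for analgesic purposes or for lytic lesions at risk of fracture, or for progression of the brain metastases may be carried out". Section 6.4.2.1 exempts this palliative radiotherapy and surgery from the rule that other anticancer therapy ends study treatment.

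**The concern.** The exclusion covers therapy received at any time on study, but its named source begins after the final dose. A patient who has brain radiotherapy or resection and then continues or resumes ceritinib has that treatment before the last dose. A programmer following SAP 2.7.1 literally would find no record of it on the named page and would keep the later scans in BOR.

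Tumour shrinkage caused by radiation or surgery could then be counted as a ceritinib response. An unconfirmed PR seen before the local treatment could also be confirmed by a scan taken after it. The endpoints at stake are those built on BOR in the brain or the whole body: OIRR, ORR, overall IDCR and DCR. A patient wrongly counted as a responder would also enter the time-to-response and duration-of-response summaries.

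**Working it through.** **Step 1. Scope of the rule against scope of the source.**

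| Item | Period covered | Place |
|---|---|---|
| BOR exclusion | Any time on study | SAP 2.7.1 |
| Brain radiotherapy counts (intracranial, whole body) | No time limit stated | SAP 4.6.1 |
| Named source | After last dose | SAP 2.7.1; Protocol 7.1.6.3 |
| Partial start dates, post-treatment therapies | Not before last dose + 1 day | SAP 4.8.4 |
| Permitted local brain therapy | Before last dose, if ceritinib continues or resumes | Protocol 4.1.2.2, 6.1.3, 6.4.1.5 |

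The SAP and protocol name the page slightly differently. I take them to be the same page, because both place it after the end of study treatment. The last row then falls outside the named source.

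Other records exist. Procedures from 28 days before first dose to 30 days after last dose go to the Surgical and Medical Procedures eCRF (Protocol 6.4; SAP 2.6). Resource-use data on the treatment of brain metastases include radiotherapy and radiosurgery (Protocol 7.2.6). Neither is named for BOR.

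**Step 2. Which readings are exposed.**

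- *A reader who has recorded PD.* CR and PR must occur before progression (SAP 2.7.1). A patient treated past progression counts as PD (SAP 2.7.3), and later assessments are ignored (Protocol Appendix 2, 14.2.17). The missing source does no harm here.
- *BIRC without PD.* Investigator and BIRC readings are separate sources (SAP 4.6.3). Nothing in the plan lets investigator PD close the BIRC's BOR, and in the two single-site exceptions of Protocol 4.1.2.2 imaging after investigator PD still goes to the BIRC. If the BIRC read no PD, scans after local brain therapy remain eligible.
- *Either reader, treatment without RECIST PD.* Clinical deterioration is not documented progression (SAP 2.7.1). While equivocal progression awaits confirmation, Protocol 4.1.2.2 leaves medically necessary action to the investigator.

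For DCR and overall IDCR the window is narrower. One SD scan more than 7 weeks after first dose is enough, so these rates change only if local therapy came before the first qualifying scan.

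The direction is upward throughout. Excluding the later scans can remove a PR, CR or SD but cannot create one.

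**Step 3. Leverage of one patient.** The exact interval for x responders among n is L = Beta⁻¹(0.025; x, n−x+1), U = Beta⁻¹(0.975; x+1, n−x). This reproduces all 13 rows of SAP Table 2-6, including the three cases used in the text of SAP 2.10:

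- 35/70 = 50%: (37.80%, 62.20%)
- 30/50 = 60%: (45.18%, 73.59%)
- 12/20 = 60%: (36.05%, 80.88%)

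One responder is worth 1/70 = 1.4 points, 1/50 = 2 points or 1/20 = 5 points. If k of the responders in those cases were misattributed (k is illustrative, not an estimate):

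| N | k | Rate | Exact 95% CI | Lower bound stated in SAP 2.10 |
|---|---|---|---|---|
| 70 | 1 | 48.6% | 36.44 to 60.83 | above 35% |
| 70 | 2 | 47.1% | 35.09 to 59.45 | above 35% |
| 70 | 3 | 45.7% | 33.74 to 58.06 | above 35% |
| 50 | 1 | 58.0% | 43.21 to 71.81 | above 45% |
| 20 | 1 | 55.0% | 31.53 to 76.94 | above 36% |

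The stated bound is lost at k=3 for N=70 and at k=1 for N=50 and N=20. The last two margins were thin to begin with (45.18 against 45; 36.05 against 36), so this shows sensitivity to single patients rather than expected harm.

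**The case against.** The strongest reply is that the rule is explicit and the source sentence only a note. SAP 2.7.1 and 4.6.1 together say that brain radiotherapy on study ends response assessment, *as appropriate* leaves room for other records, and the data are collected. A careful programmer would use them. Part of this stands: the plan does not say that the named page is the only source. But it names no other, and the qualifier does not point to one.

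A second reply is that local brain therapy follows progression, so BOR is already closed. This stands for a reader who has recorded PD, and it protects most investigator results. It does not cover a BIRC reading without PD, or treatment given without RECIST PD.

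A third is that the BIRC route is narrow. The BIRC must have read no PD. The treated lesions must include its baseline target lesions. Their sum must then be at least 30% below baseline and, unless an earlier PR is being confirmed, stay so on a second scan at least 4 weeks later. Focal treatment of a new lesion alone would not shrink baseline targets, and a new lesion that the BIRC sees is PD. All this is fair and argues for a small number, though Section 6.4.1.5 also allows radiotherapy for progressing brain metastases generally.

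A reader might go further and infer that analgesic bone radiotherapy inflates OERR or the primary ORR. The documents do not carry that. Section 6.4.1.5 requires RECIST progression to be assessed whenever palliative radiotherapy is started. Appendix 2 (14.2.4) makes blastic bone lesions non-measurable, and lytic or mixed lesions measurable only through a qualifying soft-tissue component. Bone treatment cannot affect OIRR, and whether it should end response assessment at all is debatable.

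**Conclusion.** The gap between rule and named source is real: read literally, the SAP does not carry out its own exclusion for local brain therapy given before the last dose. The exposure is mainly in BIRC-based OIRR, ORR, overall IDCR and DCR where the BIRC has not read PD, plus patients of either reader treated for clinical or equivocal progression.

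The bias, if any, is upward. Its size cannot be stated, because the documents do not say how many patients had such treatment without PD by the reader concerned. Only the per-patient leverage in Step 3 is known. A reader might be tempted to multiply assumed rates of radiotherapy, reader disagreement and shrinkage into an expected bias. None of those rates is in the documents, and such a product would also have to leave out patients whose response was confirmed before the local therapy.

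Nor should the point be read as undermining the primary result or the trial's main question. The primary endpoint is investigator-assessed whole-body ORR; OIRR is secondary, and the study is estimation only (SAP 2.7.2).

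The separate choice in SAP Table 2-2 to ignore new therapy for DOIR, DOER, DOR and PFS is deliberate and is not part of this point.

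**What to change.** In SAP 2.7.1 and 4.6.1:

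- Identify further anticancer therapy from the Surgical and Medical Procedures and Concomitant Medications eCRFs and the resource-use radiotherapy and radiosurgery data, as well as the post-treatment page, dated from first dose.
- Take the earliest on-study date of brain radiotherapy or brain surgery, whatever the dosing status, and exclude later scans from intracranial and whole-body BOR. Apply this to both investigator and BIRC readings. Extracranial BOR stays unaffected by brain treatment, as SAP 4.6.1 already provides.
- List the patients with on-treatment local brain therapy, with its date and each reader's status at that date, so that the number affected is visible.

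The cost is a few lines of SAP text, a small programming step and possibly a slightly lower response rate. It relies on data that the documents describe as collected. Before programming, confirm which of these forms actually holds on-treatment brain radiotherapy. No clinical rule changes.

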### 2.7.2 Statistical hypothesis, model, and method of analysis

The primary efficacy analysis will be performed on the FAS. This is an estimation based study and no statistical testing of hypothesis will be conducted.

The primary efficacy endpoint ORR per investigator in the whole body will be estimated and the 95% exact binomial (Clopper and Pearson 1934) confidence intervals (CIs) will be provided by study arm and for all patients. Exact binomial confidence intervals will be used since the confidence limits based on the normal approximation are not bounded by the [0, 1] interval, meaning that for rates close to 0 or 1, the upper limit of the normal approximation interval for the proportion could exceed 1 or the lower limit could be negative.

Additionally, the ORR in the whole body will also be summarized by prior radiation to the brain, prior ALK inhibitor use and overall using the data from Arms 1 through 4.

### 2.7.3 Handling of missing values/censoring/discontinuations

Confirmed PR or CR reported prior to any additional anticancer therapy will be considered as responses in the calculation of the ORR, irrespective of the number of missed assessments before response.

Patients with a best overall response (BOR) of ‘Unknown’ per RECIST 1.1 will be considered as non-responders when estimating ORR. Patients who have disease progression and continue to receive study drug after progression will qualify for PD at the time of progression and will be counted as PD in the derivation of ORR and any other efficacy endpoints.

### 2.7.4 Supportive analyses

Waterfall plots representing the best percentage change from baseline in the sum of the tumor diameters for target lesions will be produced by prior ALKi use (Yes/No) for FAS. See [Section 4.6.1](#) for details on construction of waterfall graphs.

## 2.8 Analysis of secondary variables

### 2.8.1 Efficacy

Table 2-1 summarizes all tumor related endpoints and the population for analysis. The definitions and details on the derivation of the secondary endpoints are given in the following sections. Confirmation of response is required for all response endpoints, as per RECIST 1.1 and RANO. Further details and rules needed for programmatic implementation of RECIST 1.1 guidelines and RANO guidelines are provided in Section 4.6.1 and Section 4.6.2 respectively.

**Table 2-1 Summary of tumor-related efficacy endpoints and analysis populations**

Category	Efficacy endpoints *	By investigators or BIRC	Primary analysis population#
Primary endpoint	ORR	Investigators	FAS
Key secondary endpoint	DCR	Investigators	FAS
Other secondary endpoints			
Intracranial endpoints	OIRR	Both	FAS and FAS subset**
	IDCR	Both	FAS and FAS subset**
	IDCR at week 8 and week 16	Both	FAS
	TTIR	Both	FAS and FAS subset**
	DOIR	Both	FAS and FAS subset**
Extracranial endpoints	OERR	Both	FAS
	EDCR	Both	FAS
	EDCR at week 8 and week 16	Both	FAS
	TTER	Both	FAS
	DOER	Both	FAS
Whole body endpoints	ORR	BIRC	FAS
	DCR	BIRC	FAS
	TTR	Both	FAS
	DOR	Both	FAS
	PFS	Both	FAS
	OS	N/A	FAS
Exploratory endpoints			
Intracranial endpoints	OIRR by RANO	Both	FAS subset**
	TTIR by RANO	Both	FAS subset**
	DOIR by RANO	Both	FAS subset**
	IDCR by RANO	Both	FAS

#: Efficacy endpoints per RECIST or Modified RECIST will be analyzed 1) by study arm and for all patients and 2) by prior radiation to brain and prior ALK inhibitor use and overall for patients in arm 1-4. Efficacy endpoints per RANO will be analyzed by study arm and overall for patients in arm 1-4.

\*: Efficacy endpoints are evaluated by RECIST 1.1 or Modified RECIST 1.1 unless otherwise noted.

\*\* : FAS subset with measurable brain metastases at baseline.

### 2.8.1.1 Key secondary endpoint

The key secondary objective is to evaluate Disease Control Rate (DCR). The DCR is defined as the proportion of patients with best overall response (BOR) of CR, PR or SD in the whole body, as assessed per RECIST 1.1 by the investigator.

DCR will be estimated and the exact binomial 95% CI (Clopper & Pearson, 1934) will be presented by study arm and for all patients.

### Supportive and sensitivity analyses

The DCR will also be summarized by prior radiation to the brain and by prior ALK inhibitor use.

### 2.8.1.2 Other secondary endpoints

The following intracranial, extracranial and whole body (for lesions **in and outside** the brain) tumor-response related endpoints will be assessed separately based on investigator assessment and BIRC assessment per RECIST 1.1 (OERR, EDCR, TTER, DOER, ORR, DCR, TTR, DOR and PFS) or Modified RECIST 1.1 (OIRR, IDCR, TTIR, DOIR).

